6.2.1. Inclusion criteria for the study data encoding

- All subjects enrolled in ZOSTER-006 and ZOSTER-022 (See Section 7.2 and 8.3.1)
- Subjects who died or were lost to follow-up during ZOSTER-006 and ZOSTER-022 will be considered for enrolment in ZOSTER-064 and their data/questionnaires up to that point will be used.

See Section 8.1 for site specific subject lists.

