Subjects who developed a confirmed HZ during the interval between two timepoints will be considered HZ+ at the later timepoint. Characteristics and QoL scores reported for this subject at the last timepoint before onset of HZ will be considered **leading** to HZ.

Example: A subject developed a confirmed HZ episode on Month 22:

- Subject’s characteristics and QoL scores reported at Day 0 will be considered as **not leading** to HZ.
- Subject’s characteristics and QoL scores reported at Month 14 will be considered as **leading** to HZ.

- Subject's characteristics and QoL scores reported at timepoints posterior to onset of HZ (Month 26 and Month 38) will be censored.

Further, details regarding the analysis will be provided in the statistical analysis plan.

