6.3.4. Predictive factors for subjects developing HZ

A Cox regression model allowing for time-dependent covariates will be fitted to identify which factors are predictive of developing HZ. The model will include time to HZ as the outcome variable, the demographic variables age and gender and the time dependent *SF*-36 variables and *EQ-5D* variables as potential predictors. This analysis will be performed for subjects in the Placebo group in the TVC.

Subjects who did not develop HZ will be censored at the time of their last study visit. The regression model will be used for both minimally adjusted analyses and multivariate analyses. All factors will initially be examined in an age- and gender-adjusted model with further adjustment for the original study (ZOSTER-006 or ZOSTER-022). Factors will be included in the multivariate model if they are associated (P < 0.05 using a two-sided Wald test) with HZ in the minimally adjusted model. The multivariate model will also include age, gender and original study. A step-down (backward) variable selection procedure will be used to fit the final multivariate model. This model will be fitted using the PHREG procedure of the SAS/STAT package.

The parameter estimates and standard error of each SF-36 and EQ-5D parameter from the minimally adjusted model will be presented. The final multivariate model will also be presented.

The analysis will be performed with the event defined as a HZ confirmed case. Three separate analyses will be performed examining the impact of excluding suspected but not confirmed cases.

The first analysis will exclude subjects who had a suspected case that was later proven not to be a HZ episode.

204878 (ZOSTER-064) Statistical Analysis Plan Amendment 1

The second analysis will include all subjects. Those subjects who had a suspected case that was later proven not to be a HZ episode will be censored at their latest available assessment and will be considered not to have had the event.

The third analysis will also include all subjects. The definition of event will be changed to having a suspected case of HZ.

The distribution of confirmed cases of HZ amongst suspected cases will be presented by age group for subjects in the placebo group in the TVC.

Details of the process behind the inclusion of time dependent covariates are included in section 7.4

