7.4. Predictive factors for individuals developing HZ

Only subjects in the placebo group will be included in the analysis of potential predictive factors. A Cox regression model allowing for time-dependent covariates will be fitted to identify which factors are predictive of developing HZ. The model will include time to HZ as the outcome variable, the demographic variables age and gender and the *SF-36* variables and *EQ-5D* variables as potential predictors.

Each EQ-5D and SF-36 assessment at a scheduled time point will be re-classified into time points based on the date of assessment relative to date of vaccination:

Studyday=date of assessment – date of vaccination.

The study day will be time component used in the model.

Since there are a maximum of four SF-36 and EQ-5D assessment times we define the variables T_0 , T_1 , T_2 , T_3 as the study day relative to vaccination (day 0) of the QoL assessment and QoL₀ QoL₁, QoL₂, QoL₃ as the values of the QoL assessment at each timepoint. The value of the time-dependent variable QoLt is equal to QoL₀ if $0 < t \le T_1$, QoL₁ if $T_1 < t \le T_2$, QoL₂ if $T_2 < t \le T_3$, with QoLt = QoL₃ if $t > T_3$.

The above model is implemented in SAS as follows:

```
ODS output ParameterEstimates=PE1;

PROC PHREG DATA=tsurv;

CLASS study gender;

MODEL fu_time*hz_conf(0) = age study gender PFT;

PFT=PF0;

IF fu_time > time1 and time1 ne . then PFT=PF1;

IF fu_time > time2 and time2 ne . then PFT=PF2;

IF fu_time > time3 and time3 ne . then PFT=PF3;

RUN;
```

Spearman correlations coefficients will be presented to display the relationships between pairs of variables. In addition, for the quality of life variables, the variance inflation factor and the condition indices for testing multicollinearity will be estimated.

Example: To illustrate the method the following hypothetical 3 subjects are examined:

Table 5 Data from hypothetical subjects to illustrate time dependent covariates

Subject	QoL0	T0	QoL1	T1	QoL2	T2	QoL3	Т3	Censored /day	Event/ day
PPD	80	0	75	425	65	790	24	1050	Yes/1090	No
	90	0	65	420	50	800	45	1050	No	Yes/480
	98	0	43	435	45	790	45	1060	No	Yes/900

204878 (ZOSTER-064)

Statistical Analysis Plan Amendment 1

Table 6 Resolution of hypothetical subject

Subject PPD	Event	Time Interval	QoL
PPD	0	(0, 425]	80
	0	(425, 790]	75
	0	(790, 1050]	65
	0	(1050, 1090]	24

Subject will be censored at day 1090.

Table 7 Resolution of hypothetical subject

Subject	Event	Time Interval	QoL
PPD	0	(0, 420]	90

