	1	(420, 480]	65

Subject had the HZ episode on day 480. The QoL assessment on day 420 is considered as leading to the HZ episode. The subsequent QoL assessments will not be included in the analysis.

Table 8 Resolution of hypothetical subject

Subject	Event	Time Interval	QoL
PPD	0	(0, 435]	98
	0	(435, 790]	43
	1	(790, 900]	45

Subject had the HZ episode on day 900. The QoL assessment on day 790 is considered as leading to the HZ episode. The subsequent QoL assessment at day 1060 will not be included in the analysis.

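### The HZ predictor model censors non-cases at their last study visit but times cases at onset, which can slightly bias the hazard ratios if exit rates differ by quality of life

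*SAP*

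**What the plan says.** SAP 6.3.4 fits a Cox model with time-dependent SF-36 and EQ-5D covariates to placebo subjects in the TVC. For non-cases the rule is: "Subjects who did not develop HZ will be censored at the time of their last study visit". Protocol 10.7.6.3 gives the same rule. In the second of the three planned analyses, subjects whose suspected case proved not to be HZ "will be censored at their latest available assessment and will be considered not to have had the event".

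Cases are timed at onset. The Protocol's illustration reads "Example: A subject developed a confirmed HZ episode on Month 22", which lies between the Month 14 and Month 26 timepoints. SAP 7.4 says of one worked subject: "Subject had the HZ episode on day 480. The QoL assessment on day 420 is considered as leading to the HZ episode"; that subject's next assessment is on day 800. A third worked subject has the event on day 900, between assessments on days 790 and 1060.

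The only worked non-case has a last QoL assessment on day 1050, and the SAP says "Subject will be censored at day 1090".

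The time variable appears in the code as "MODEL fu_time*hz_conf(0) = age study gender PFT". Neither fu_time nor the term for the last visit is defined.

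Early leavers are in the data. Protocol 6.2.1 says: "Subjects who died or were lost to follow-up during ZOSTER-006 and ZOSTER-022 will be considered for enrolment in ZOSTER-064". Protocol 10.6.1 supposes that censoring is independent of the endpoint.

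**The concern.** After a subject's last visit, the rule treats the same stretch of time in two ways. If HZ occurs there, the time and the event are kept. If the subject is observed without HZ and then dies or withdraws, the time is removed. The censoring date thus depends on what happened after it, which conflicts with the independence supposed in Protocol 10.6.1. This holds even when exit itself is unrelated to HZ.

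Risk sets between visits become too small, and most so where exit is frequent. The candidate predictors are SF-36 and EQ-5D scores. Poor scores may go with more deaths and dropout, although the documents give no rates. If they do, poor QoL could look slightly predictive of HZ when it is not. Candidates enter the multivariate model at P<0.05 without multiplicity adjustment, so the bias could carry into variable selection. The three planned analyses vary only the handling of suspected but unconfirmed cases, so none of them tests the censoring date.

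**Working it through.** **Reproducing the plan's own figures.** Applying the SAP 7.4 covariate rule to Table 5 returns Tables 6 to 8 exactly:
- Subject 1: (0,425], (425,790], (790,1050], (1050,1090], no event.
- Subject 2: (0,420], (420,480], event.
- Subject 3: (0,435], (435,790], (790,900], event.

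Cases are therefore timed at onset. The censored subject is followed for 1090 − 1050 = 40 days past the last QoL form.

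**Inputs.**
- QoL timepoints at Months 0, 14, 26 and 38 (SAP 6.3.1).
- HZ rate of 10 per 1000 person-years (Protocol 1.1.1, age 60 and over).
- Assumed, because not in the documents: constant exit rates d0 and d1 per year in a low-exit and a high-exit group; true hazard ratio 1; 500 to 900 placebo events; 20% of subjects in the high-exit group.
- Worst-case reading: visits occur only at the QoL timepoints, and every leaver was observed HZ-free until exit.

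**Formula.** Under the stated rule the apparent hazard at time t is the true hazard × exp(d × (next visit − t)). The spurious hazard ratio is then about exp((d1 − d0) × w), where w is the mean wait to the next visit:

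w = (14² + 12² + 12²) / (2 × 38) = 484 / 76 = 6.37 months = 0.531 years.

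For type I error, c = ln(HR) × √(D × p × (1 − p)) and α = 1 − Φ(1.96 − c) + Φ(−1.96 − c), with D events and p = 0.20.

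| Exit per year, low vs high | Hazard inflated by (simulated) | Spurious HR (formula) | Two-sided α, 500 to 900 events |
|---|---|---|---|
| 2% vs 4% | 1.1% vs 2.2% | exp(0.02 × 0.531) = 1.01 | 0.051 to 0.052 |
| 3% vs 10% | 1.6% vs 5.5% | exp(0.07 × 0.531) = 1.04 | 0.063 to 0.073 |
| 5% vs 20% | 2.7% vs 11.5% | exp(0.15 × 0.531) = 1.08 | 0.110 to 0.159 |
| 5% vs 5% | 2.7% vs 2.7% | 1.00 | 0.050 |

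**Simulation check.** Two million subjects were simulated per scenario and a Cox model fitted. Dividing the last-visit hazard ratio by the correctly censored one from the same draws gives 1.013/1.002 = 1.01, 1.030/0.992 = 1.04 and 1.097/1.010 = 1.09, close to the formula. With censoring at actual exit, the hazard ratio was 0.99 to 1.01 in all four scenarios.

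**Closer visits.** Adding visits at Months 2 and 3 (Month 2 is assumed) gives w = (2² + 1² + 11² + 12² + 12²) / 76 = 414 / 76 = 5.45 months. The three unequal-exit hazard ratios fall to about 1.01, 1.03 and 1.07.

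**How extreme the last unequal scenario is.** At 15% per year, 1 − exp(−0.15 × 38/12) = 38% of the group has left by Month 38. At 20% the figure is 47%.

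**The case against.** The strongest reply is that the documents do not show how far back a non-case is cut. A reader might infer that a subject lost at Month 24 is returned to the Month 14 questionnaire. The SAP speaks of a study visit, not a questionnaire, and its one censored example ends 40 days after the last form. The full visit and contact schedule sits in the parent protocols. If visits fall between the QoL timepoints, the gap and the bias shrink. This stands, and the figures above are upper-end for their exit rates.

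Second, where nothing was observed after the last visit, censoring there is correct. The bias comes only from subjects seen HZ-free beyond it. This also stands, and the split between deaths, withdrawals and losses is not given.

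Third, a reader might infer the same loss for suspected but unconfirmed subjects in the second analysis. That is not shown. Protocol section 5 describes rash sampling and committee referral, so their latest assessment may be an off-schedule contact. They are also few: Protocol 10.4 expects about 1000 suspected cases in both groups together, confirmed ones included.

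Fourth, the model adjusts for age, gender and study and updates QoL over time. Only exit differences that remain after this matter. The analysis is also exploratory, and Protocol 10.8 asks for cautious interpretation.

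These points limit the size. They do not remove the unequal treatment of cases and non-cases, or supply the missing definition of fu_time.

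**Conclusion.** The point holds as a modest defect. The stated rule drops HZ-free time after the last visit for non-cases only, so the HZ hazard is somewhat overstated, more so where exit is frequent. The hazard ratios are biased if exit differs by QoL level after adjustment, and unbiased if it does not. Completers are unaffected if their last visit is study end.

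Under the assumed exit rates and the widest visit gaps, the spurious hazard ratio is about 1.01 (2% vs 4% per year) to 1.04 (3% vs 10%). A reader might infer a distortion nearer 1.08 and a clearly raised false-positive rate. That needs about 20% annual exit in one group, which nothing in the documents supports.

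**What to change.** In SAP 6.3.4, define fu_time for non-cases in the placebo TVC as the last date under HZ surveillance and known to be HZ-free: the earliest of death, withdrawal, last contact with HZ ascertainment, or study end. Use the same date for suspected but unconfirmed subjects in the second analysis, in place of the latest available assessment. Keep last-visit censoring as a sensitivity analysis, and list the departure from Protocol 10.7.6.3 in SAP section 9.

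Derive the date for all placebo TVC subjects. The follow-up time behind the efficacy and BOI analyses (SAP 6.3.2 and 6.3.3) covers the mTVC under parent-SAP rules that are not shown here and might themselves end at the last visit. It should not be carried over unchecked.

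The cost is a few sentences of SAP text, one extra model run, and a small derivation for subjects in the TVC but not the mTVC. Deaths are documented in the parent databases (Protocol 8.3.3), and consent-withdrawal dates are on the subject lists (Protocol 8.1). Whether a last-contact date with HZ ascertainment is held for everyone has to be confirmed in the parent data.

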10.7.6.3. Predictive factors for individuals developing HZ

Only subjects in the placebo vaccination group will be included in the analysis of potential predictive factors. A Cox proportional hazards regression model allowing for time-dependent covariates will be fitted to identify which factors are predictive of developing HZ. The model will include time to HZ as the outcome variable and as potential predictors: demographic and clinical characteristics, *SF-36* variables and *EQ-5D* variables. Subjects who did not develop HZ will be censored at the time of their last study visit. The proportional hazards regression model will be used for both minimally adjusted analyses and multivariate analyses. All factors will initially be examined in an age- and sex-adjusted model with stratification for the clinical trial (i.e. ZOSTER-006 and ZOSTER-022). Factors will be included in the multivariate model if they are associated ($P < 0.05$ using a two-sided test) with HZ in the minimally adjusted model. The multivariate model will also include age and gender with stratification for the clinical trial (i.e. ZOSTER-006 and ZOSTER-022). A step-down (backward) variable selection procedure will be used to fit the final multivariate model. This model will be fitted using the PHREG procedure of the *SAS/STAT* package.

Spearman correlations coefficients will be presented to display the relationships between pairs of variables. In addition, particularly for the quality of life variables, the variance inflation factor and the condition indices for testing multicollinearity will be estimated.

In the analysis, the impact of excluding “suspected but not confirmed cases” of HZ will be explored. Three analyses will be performed whereby it will be assumed that “suspected but not confirmed cases” are (1) “Not in at risk group” (2) “In at risk group” and event=0, (3) “In at risk group” and event=1.

Due to the multiple measurements of the *EQ-5D* and *SF-36* over time, repartition in the HZ positive or HZ negative will be dynamic. Subjects who did not develop a confirmed HZ before one-timepoint (Day 0, Month 14, Month 26 and Month 38) will be considered HZ negative at that timepoint, and the characteristics and QoL scores reported for this subject at the previous timepoint will be considered as **not leading** to HZ.

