6.3. Secondary Objectives

6.3.1. SF-36 and EQ-5D

The quality of life questionnaires to be analysed in this study are the SF-36 and EQ-5D. The SF-36 health survey and the EQ-5D questionnaires were to be completed by all subjects at Months 0, 14, 26 and 38 in ZOSTER-006 and ZOSTER-022.

Basic summary statistics (N, Mean, Standard Deviation) of each of the 8 components of the SF-36 Questionnaire (Physical Functioning, Role Physical, Bodily Pain, General Health, Vitality, Social Functioning, Role Emotional and Mental Health) and the EQ-5D Utility and visual analogue scale (VAS) scores will be presented at each scheduled timepoint by country and age group.

In addition, a more detailed statistical analysis, including the median, quartiles and minimum and maximum values, of the 10 components will be presented by timepoint, age-category and gender and will be presented in a separate annex.

The EQ-5D utility will be based on country specific Time Trade-off (TTO) values for the analysis by country. The UK TTO will be used for countries for which there is no specific TTO.

Presenting the data by country will allow for comparison with normative values for those questionnaires in the general population of the countries participating in the study

This analysis will be based on the TVC.

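### The Cox model for predictors of HZ pools up to 18 countries with no country term, so between-country differences could be screened in as predictors for individuals; the protocol's stratification by trial was also dropped without being declared

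*SAP*

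**What the plan says.** The predictor analysis is a Cox model with time-dependent QoL covariates, fitted in placebo subjects of the pooled TVC (SAP 6.3.4). Its candidates are "the demographic variables age and gender and the time dependent" SF-36 and EQ-5D variables.

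- **First step (SAP 6.3.4).** "All factors will initially be examined in an age- and gender-adjusted model with further adjustment for the original study (ZOSTER-006 or ZOSTER-022"). A variable with P<0.05 on a two-sided Wald test goes forward.
- **Second step (SAP 6.3.4).** Backward selection follows. "The multivariate model will also include age, gender and original study".
- **Code (SAP 7.4).** "CLASS study gender" and "MODEL fu_time*hz_conf(0) = age study gender PFT", where PFT is the current value of one scale, used as the example. There is no STRATA statement.
- **Protocol 10.7.6.3.** Trial is a stratification factor in both steps. For the second: "The multivariate model will also include age and gender with stratification for the clinical trial". Country is not mentioned there either.
- **Countries (SAP Table 2).** 9 in Europe, 5 in Australasia, 2 in Latin America and 2 in North America: 9 + 5 + 2 + 2 = 18. Fewer may contribute, because SAP 5.1 keeps only centres that take part in ZOSTER-064.
- **QoL by country (SAP 6.3.1).** "Presenting the data by country will allow for comparison with normative values for those questionnaires in the general population of the countries".

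**The concern.** The objective is to find factors that predict HZ in individuals. A model that pools countries without separating them estimates a mixture of two associations: the one between subjects within a country, and the one between country averages. If countries whose subjects report worse QoL also have more HZ, or detect it more completely, the second can move a scale's coefficient when the first is zero. It can also mask a real within-country association. Original study has only two levels and cannot stand in for country.

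A shift in the Wald statistic matters here because P<0.05 decides which scales enter the multivariate model. None of the planned checks would reveal it:

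- The three variants in SAP 6.3.4 differ only in how suspected but unconfirmed cases are treated.
- The variance inflation factors and condition indices address collinearity among QoL variables.
- The bootstrap in Protocol 10.7 resamples the same pooled data, so it would reproduce a between-country association.

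The change in how trial is handled is a separate matter. A study covariate assumes proportional baseline hazards between a trial in people aged 50 and over and one in people aged 70 and over (Protocol 1.1.2). Stratification does not.

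**Working it through.** The plan states no power or effect size for this model, so there is no figure to reproduce. The check asks how far the P<0.05 screen could be disturbed when no scale has any within-country effect.

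**Inputs from the documents.** 18 listed countries (SAP Table 2). Two-sided 0.05 screen (SAP 6.3.4). About 30,000 subjects and about 1000 suspected HZ cases, both arms together (Protocol 10.4).

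**Assumptions.**

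- About 15,000 placebo subjects, since the allocation ratio is not given.
- 400 or 700 confirmed placebo events. The 1000 covers both arms and includes unconfirmed cases.
- ICC, the between-country share of QoL variance: 0.02 to 0.10.
- s, the between-country SD of the log HZ rate: 0.1 to 0.3. A country 1 SD above average then has exp(0.1) = 1.11 to exp(0.3) = 1.35 times the average rate.
- r, the country-level correlation of worse QoL with a higher HZ rate: 0.5 or 0.

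**Formula.** Spurious log HR per SD: b = r × s × √ICC. Standard error about 1/√events. Shift in z = b × √events. False-positive rate = Φ(−1.96 − shift) + 1 − Φ(1.96 − shift).

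Example: r = 0.5, s = 0.3, ICC = 0.10 gives b = 0.5 × 0.3 × 0.316 = 0.0474. The HR per SD of better QoL is exp(−0.0474) = 0.954, or 1/0.954 = 1.05 per SD of worse QoL. At 700 events the shift is 0.0474 × 26.46 = 1.25, and the rate is 24.1%.

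| ICC | s | HR per SD (r = 0.5) | z shift, 400 / 700 events | False positives, 400 / 700 events |
|---|---|---|---|---|
| 0.02 | 0.1 | 0.993 | 0.14 / 0.19 | 5.2% / 5.4% |
| 0.05 | 0.2 | 0.978 | 0.45 / 0.59 | 7.3% / 9.1% |
| 0.05 | 0.3 | 0.967 | 0.67 / 0.89 | 10.3% / 14.4% |
| 0.10 | 0.3 | 0.954 | 0.95 / 1.25 | 15.8% / 24.1% |

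**Simulation.** 18 equal-sized countries, 15,000 subjects, 2000 runs per setting, score test with a fixed covariate and no age, gender or study terms.

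| ICC | s | Events | r = 0, pooled | r = 0.5, pooled | r = 0.5, stratified by country |
|---|---|---|---|---|---|
| 0.02 | 0.2 | 400 | 4.6% | 5.9% | 4.9% |
| 0.05 | 0.3 | 400 | 6.0% | 11.0% | 4.4% |
| 0.10 | 0.3 | 400 | 7.4% | 16.2% | 5.8% |
| 0.02 | 0.2 | 700 | 4.7% | 7.1% | 5.2% |
| 0.05 | 0.3 | 700 | 6.4% | 15.6% | 5.0% |
| 0.10 | 0.3 | 700 | 7.8% | 25.4% | 4.0% |

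The simulation error at 5% is √(0.05 × 0.95/2000) = 0.5 percentage points. At r = 0 the pooled rate can still exceed 5%, because the realised correlation across 18 countries is rarely exactly zero. Stratified rates stayed between 3.8% and 5.8% in every setting run.

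**Cost of stratifying.** It discards the between-country share of the covariate's variance, so the standard error rises by about 1/√(1 − ICC): 1.01 at ICC 0.02 and 1.05 at ICC 0.10. With at most 2 × 18 = 36 strata, 15,000/36 is about 417 subjects each if they are equal in size, so small risk sets cost little more.

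**The case against.** The strongest reply is that nothing in the documents shows a country effect. A reader might infer from SAP 6.3.1 that the study itself treats QoL scores as differing by country. It does not say so. It says that presentation by country permits comparison with national norms. Country-specific values apply only to the EQ-5D utility and only in the by-country analysis. Protocol 10.7.3 names the UK value set for the main analysis, and Protocol 10.7.2 scores the SF-36 with one standard algorithm. No passage says that HZ incidence or ascertainment varies by country. Protocol 1.1.1 does list race among suggested factors, but that would argue for a race term, not country strata. All of this stands, and it is why the size can only be given as a range that begins near nil.

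A reader might also infer that the SAP abandoned a protocol requirement on country. It did not: the protocol omits country too. The departure concerns trial only, and the figures above do not measure its effect.

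It can further be said that a pooled association may predict well without holding within countries, and that the analysis is secondary and exploratory, with no multiplicity adjustment (Protocol 10.7) and a general caution on interpreting its descriptive comparisons (Protocol 10.8). This lowers the stakes. It does not remove the point, because the objective and rationale concern characteristics of individuals, and the plan has no check that would tell the two kinds of association apart.

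**Conclusion.** The omission is certain: neither the SAP text nor its code separates countries, and no planned analysis would expose a between-country contribution. Its effect is conditional on both QoL responses and HZ incidence or ascertainment varying by country. Under the stated assumptions the per-scale false-positive rate is about 5% to 24% at a country-level correlation of 0.5, and 5% to 8% at zero correlation. The spurious HR is at most about 1.05 per SD. The documents do not support saying that the results will be biased, or fixing one figure within that range.

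The undeclared move from stratification by trial to a study covariate needs no assumption. Protocol 10.7.6.3 and SAP 6.3.4 and 7.4 differ, and SAP section 9 is silent on it.

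This is a worthwhile, inexpensive improvement to a secondary exploratory analysis. It does not touch the primary frailty objective.

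**What to change.** In SAP 6.3.4, state that the minimally adjusted and multivariate models are stratified by trial and country. In SAP 7.4, add `STRATA study country;` and remove `study` from the CLASS and MODEL statements. PHREG accepts this alongside the programming statements that define the time-dependent covariate. No rule for merging small countries into regions is needed, because a stratum without events contributes nothing to the partial likelihood. Record the addition of country in SAP section 9, since the protocol stratifies by trial alone.

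At minimum, restore `STRATA study;` as the protocol requires, and prespecify the country-stratified model as a sensitivity analysis reported beside the main one.

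The cost is one line of code and a few sentences. Country is already used for other tables. The loss of precision is small, roughly 1% to 5% on the standard error under the ICC values above. The coefficients will then describe within-country association only, and the report should say so.

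### The protocol stratifies the HZ predictor model by trial; the SAP text and code enter trial as a covariate without declaring the change (minor)

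*SAP*

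**What the plan says.** Protocol 10.7.6.3 covers both modelling steps. For the minimally adjusted step: "All factors will initially be examined in an age- and sex-adjusted model with stratification for the clinical trial". For the next step: "The multivariate model will also include age and gender with stratification for the clinical trial".

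SAP Amendment 1, section 6.3.4, words both steps differently. The first becomes: "All factors will initially be examined in an age- and gender-adjusted model with further adjustment for the original study". The second becomes: "The multivariate model will also include age, gender and original study". A backward procedure then gives the final model. Entry to the multivariate step is decided by a fixed cut on the first-step results: "Factors will be included in the multivariate model if they are associated (P < 0.05 using a two-sided Wald test) with HZ".

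The PHREG code in SAP 7.4 contains "CLASS study gender" and "MODEL fu_time*hz_conf(0) = age study gender PFT". It has no STRATA statement.

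SAP section 9 lists four changes from the planned analyses: QoL timepoints, cohort definitions, the description of SAEs and pIMDs, and the placement of QoL tables. None concerns this model.

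**The concern.** The two specifications are different models. With stratification each trial has its own unspecified baseline hazard. With study as a covariate there is one baseline hazard, and the two trials differ by a constant factor throughout follow-up, after adjustment for age and gender. The SAP plans no check of that.

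The trials recruited different populations: 50 years and older in ZOSTER-006, 70 years and older in ZOSTER-022 (Protocol 1.1.2). The SF-36 and EQ-5D scores are updated over time. If the trial hazard ratio changes over follow-up and scores also fall faster in one trial than in the other, part of the unmodelled trial-by-time difference can be absorbed by the QoL coefficient. That coefficient and its P value decide which factors are carried forward.

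There is a second, structural point. SAP 6.3.4 does not say that age, gender and study are kept in the model during backward selection. A covariate can be eliminated; a stratification variable cannot.

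**Working it through.** **1. Text against text**

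| Place | Minimally adjusted model | Multivariate model |
|---|---|---|
| Protocol 10.7.6.3 | stratified by trial | stratified by trial |
| SAP 6.3.4 | adjusted for study | study listed with age and gender |
| SAP 7.4 code | study in CLASS and MODEL, no STRATA | not shown |
| SAP section 9 | not mentioned | not mentioned |

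Taken alone, the SAP's word for adjustment could loosely include stratification. The multivariate sentence and the code rule that out. The November 2018 SAP, superseded but included in the same document, still had stratification in its text while its code already had study in MODEL. Amendment 1 therefore brought the text into line with the code, not with the protocol.

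**2. The models**

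- Protocol: h(t) = h_s(t) × exp(a·age + g·gender + b·QoL(t)), with a separate h_s for each trial s.
- SAP: h(t) = h_0(t) × exp(c·study + a·age + g·gender + b·QoL(t)).

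The SAP model is the special case in which the ratio of the two trial baselines is the constant exp(c). Bias in b through this route needs that ratio to vary over time and the QoL time course to differ between trials, both together.

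**3. Size**

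The documents give no figure that depends on this choice, so there is nothing to reproduce. The following is an illustration only. Every input is assumed: 15,000 placebo subjects, four one-year periods, score SD 20, true log hazard ratio -0.050 per 10 points, and a score falling per year by 2 points in ZOSTER-022 and 0.8 in ZOSTER-006 (slow), or by 5 and 2 (fast). A piecewise Poisson model with period effects plus study stands for the covariate form. Period-by-study effects stand for stratification.

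The standard error follows from the expected z of 2.46 under stratification: 0.050 / 2.46 = 0.0203 per 10 points. Per SD this is 0.0203 × 2 = 0.0406, which corresponds to roughly 1 / 0.0406² ≈ 607 confirmed placebo events. That is compatible with the approximately 1000 suspected cases over both arms in Protocol 10.4.

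| Trial hazard ratio over 4 years | Decline | Covariate form | Stratified | Shift / SE |
|---|---|---|---|---|
| 1.4 to 0.8 | slow | -0.0483 | -0.050 | 0.0017 / 0.0203 = 0.08 |
| 1.4 to 0.8 | fast | -0.0459 | -0.050 | 0.0041 / 0.0203 = 0.20 |
| 2.0 to 0.6 | slow | -0.0469 | -0.050 | 0.0031 / 0.0203 = 0.15 |
| 2.0 to 0.6 | fast | -0.0421 | -0.050 | 0.0079 / 0.0203 = 0.39 |
| constant | either | -0.050 | -0.050 | 0 |

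In the most extreme row the expected z falls from 2.46 to 0.0421 / 0.0203 = 2.07. With a score SD of 10 the shifts are 0.15 to 0.77 SE. Stratifying raises the standard error by less than 1% at SD 20 and by up to about 1.5% at SD 10.

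**4. Non-proportional hazards alone**

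A separate Cox simulation had 3000 placebo subjects, about 320 to 335 events, a log hazard ratio of -0.20 per SD and no difference between trials in QoL decline. With Weibull shapes 0.7 and 2 in the two trials, the mean estimate was -0.1840 with study as covariate and -0.1845 with strata. The largest difference in any one replicate was 0.0064, or 0.0064 / 0.0556 = 0.12 SE. Non-proportional trial hazards without differential QoL decline therefore do very little.

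**The case against.** **The effect is small and its conditions are unsupported.** Nothing in the documents suggests that the trial hazard ratio drifts, or that QoL falls faster in one trial. Both trials started in 2010, and QoL was scheduled at the same months in both. Age is in every model, so only the trial difference left after age has to be proportional. All of this stands and sets the severity. One part does not carry over: the shift is towards the null in the table only because the assumed hazard ratio falls. If it rose, the sign would reverse.

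**The analysis is exploratory.** Protocol 10.7 makes no multiplicity adjustment, and 10.8 calls comparative analyses descriptive. Univariate screening followed by backward selection is probably a larger source of instability than this choice. This also stands.

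**Silence in section 9 may not be a breach.** A reader might infer that the SAP violates the protocol's rule on changes. It does not follow: Protocol 10.9 asks for changes to be described and justified in the final study report, which can still be done. What remains is that section 9 declares matters as small as table placement but not this one, and that neither document gives a reason that the report could repeat.

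**Stratification is not free of assumptions.** It still requires proportional hazards for age, gender and QoL, and common coefficients in both trials. It removes only the assumption about trial. Covariate adjustment is a standard alternative and is acceptable if declared and checked.

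**Conclusion.** The discrepancy is real and lies in current text: the protocol stratifies by trial in both models, while the SAP text and code fit a proportional covariate without declaring or justifying it. The change adds an assumption and, as written, does not protect study from backward elimination.

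A reader might go further and infer that the predictor results would be materially biased. The documents do not support that. A shift of about 0.1 to 0.4 SE needs non-proportional trial hazards and differential QoL decline together, and both are assumed here, along with the SD of 20. With an SD of 10 it could reach 0.77 SE; with proportional trial hazards it is zero. The practical risk is limited to factors close to P = 0.05 at screening. Severity: minor.

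**What to change.** Preferred:

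- In SAP 6.3.4, state that the minimally adjusted and multivariate models are stratified by original study.
- In the SAP 7.4 code, remove study from CLASS and MODEL and add `STRATA study;`.
- Apply the same to the multivariate model and to all three suspected-case analyses.

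This takes two phrases and a line or so of code, and no new data. The downside is that no study coefficient is estimated, which is not a target of this objective, and that the standard error rises by roughly 1%.

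Alternative, if the covariate is kept: declare and justify it in SAP section 9 and carry the statement into the study report, state that study is forced into the multivariate model, and add a check of proportional hazards for study. Either route makes protocol, SAP text and code reconcilable.
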